### 7.3.11 Organs at risk

All lesion-specific organs at risk (OAR) must be contoured. The specific OAR to be contoured will depend on the location of lesion to be treated. The contour of structures that have a lumen (bronchus, trachea, esophagus, etc.) will include both the “wall” and the “lumen” to result in a cylindrical structure. In general, OAR within 5 cm of any lesion should be contoured. To identify these OARs, all PTVs will be expanded by 5 cm and any OAR that overlaps with PTV + 5 cm must be contoured.

### 7.3.12 Critical Organ Dose-Volume Limits

Dose distributions of organs at risk are critical to understand toxicity following SBRT. To facilitate planning, dose should be calculated on a single CT scan simultaneously with in-plane resolution of at least 2 x 2 x 3mm. Dose-volume histograms will be generated to evaluate dose to critical organs at risk.

### 7.3.13 Planning priorities for Organs at Risk

The spinal cord doses are absolute limits. Some OARs (i.e., the esophagus, trachea, bronchi and heart within the lung) may be situated adjacent to the treated GTV/PTV. As such, there is no specified limit as tumors that are immediately adjacent to that organ will not be able to be treated to the prescription doses without irradiating a small volume of that organ to the prescribed dose. In such a case, the planning must be accomplished so that there is no hot spot within that organ, even if that organ is part of the GTV/PTV, i.e., that no part of any serial OAR receives more than 105% of the prescribed dose. In addition, the volume of the OAR in question needs to be minimized, both in length and in the width (i.e., circumference), with efforts made to reduce the dose to the contralateral wall of the organ. For parallel OAR, exceeding the doses by more than 110% of the prescribed dose will be considered unacceptable. For non-spinal cord OAR with known sensitivity to high doses of radiation (including the bowel, esophagus, and stomach) included within a PTV or immediately adjacent to PTVs, a prescription dose at the lower end of acceptable variation should be used. Additionally, every effort should be made to cover the GTV with the prescription dose while ensuring rapid fall off to the organ at risk. Coverage of a section of PTV including or immediately adjacent to the OAR may be as low as 70% of the prescription dose ONLY in this situation. Every effort should be made to cover 100% of the GTV by the prescription dose at the lower end of acceptable variation. For tumors that are not immediately adjacent to any OAR, centers are encouraged to observe prudent treatment planning principles in avoiding unnecessary radiation exposure to critical normal structures; we expect that the OAR doses will be as low as achievable (ideally, < 6 Gy/fraction).

**Table 6: Modified AAPM Task Group 101 dose constraints for 5 fractions**

Serial Organ	Volume	Volume Dose (Gy)	Avoidance Endpoint (≥ Grade 3)
Spinal Cord	0.03 cc	30	Myelitis
	0.35 cc	23	
	1.2 cc	14.5	
Ipsilateral Brachial Plexus	0.03 cc	30.5	Brachial Plexopathy
	3 cc	27	
Cauda Equina	0.03 cc	32	Neuritis
	5 cc	30	
Sacral Plexus	0.03 cc	32	Neuropathy
	5 cc	30	Neuritis
Trachea and Ipsilateral Bronchus	0.03 cc	40	Stenosis/Fistula
	4 cc	16.5	
Esophagus	0.03 cc	35	Stenosis/Fistula
	5 cc	19.5	
Heart/Pericardium	0.03 cc	38	Pericarditis
	15 cc	32	
Great vessels	0.03 cc	53	Aneurysm
	10 cc	47	
Skin	0.03 cc	39.5	Ulceration
	10 cc	36.5	
Stomach	0.03 cc	32	Ulceration/Fistula
	10 cc	18	
Duodenum	0.03 cc	32	Ulceration
	5 cc	18	
	10 cc	12.5	
Jejunum/Ileum	0.03 cc	35	Enteritis/obstruction
	5 cc	19.5	
Colon	0.03 cc	38	Colitis/Fistula
	20 cc	25	
Rectum	0.03 cc	38	Proctitis/Fistula
	20	25	
Bladder	0.03 cc	38	Cystitis/Fistula
	15 cc	18.3	
Ureter	0.03 cc	45	Stenosis
Femoral head	10 cc	30	Necrosis
Bile Duct	0.03 cc	41	Stenosis
Renal hilum/Vascular Trunk	< 2/3 volume	23	Malignant Hypertension
Chest Wall	1 cc	45	Pain/Necrosis
	5 cc	40	
Rib	0.03 cc	43	Pain or Fracture
	1 cc	35	

Parallel Organ*	Volume	Volume Dose (Gy)	Avoidance Endpoint
Lung (total)	< 37% lung volume	13.5	Pneumonitis
	<1500 cc	12.5	Basic Lung Function
	<1000 cc	13.5	Pneumonitis
Renal cortex	< 200 cc	17.5	Basic Renal Function
Liver	<700 cc	15	Basic Liver Function

Note: Every effort should be made to avoid circumferential irradiation. Doses to serial OAR up to and including 105% of the dose prescribed to the PTV will be an acceptable variation. Doses to parallel OAR up to 110% of the values listed in the table will be an acceptable variation.

\*ClearCheck: **For parallel organs dose constraints shall include the Minimal Volume Spared (MVS); for example, MVS1350cGy  $\geq$  1000cc for Lung (total).**

### 7.3.14 Documentation requirements

In general, treatment interruptions should be avoided by preventative medical measures and supportive therapies. Treatment breaks, including indications, must be clearly documented in the treatment record.

### 7.3.15 Compliance Criteria

#### 7.3.15.1 Treatment Duration

Treatment duration will be defined per lesion. Per Protocol, all five fractions of radiation should be completed within 2-3 weeks of first radiation dose (>3 weeks is an unacceptable variation).

#### 7.3.15.2 PTV Dosimetry Compliance

Acceptable variations in the protocol prescription dose (dose covering 95% of the PTV) should be evaluated for each lesion. Prescription doses outside of the variation acceptable range will be scored as Deviation Unacceptable. Scoring of PTV coverage will be: acceptable if  $\geq$  95%, variation acceptable if 70-95%, deviation unacceptable if < 70%.

#### 7.3.15.3 Organ at Risk Dosimetry Compliance

Critical structure doses should be based on composite dose distribution when more than one met is treated. Respect spinal cord, cauda equina, sacral plexus and brachial plexus dose constraints. Any dose to spinal cord, cauda equina, sacral plexus above that listed in the above Tables will be considered an unacceptable deviation. For all other OAR, when OAR dose criteria cannot be accomplished by following planning priorities, doses to serial OAR of more than 105% of the dose prescribed to the PTV will be Unacceptable Deviations. Doses to parallel OAR exceeding 110% of the dose prescribed to the PTV will be scored as unacceptable deviations. Doses in the range between the numbers in the tables and unacceptable deviation will be considered acceptable variations.

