1. Normalization: The treatment plan should be initially normalized such that 100% corresponds to the maximum dose within the PTV (MAXPTV). While this point will typically correspond to the PTV center of mass, it can be located elsewhere within the PTV.
2. Prescription Isodose Surface Coverage: The prescription isodose surface will be chosen such that 95% of the target volume (PTV) is conformally covered by the prescription isodose surface. Doses less than 95% of the prescription dose are restricted to the outside edges of the PTV. The prescription isodose surface selected MUST be  $\geq 60\%$  and  $\leq 90\%$  of the dose maximum within the PTV (MAXPTV). The MAXPTV corresponds to the normalization point (100%) of the plan as noted in number 1 above.
3. Target Dose Heterogeneity: Rather than prioritizing target dose homogeneity, SBRT treatment planning prioritizes adequate minimum target coverage and rapid dose fall-off gradients outside of the target. Hot spots within targets are generally accepted without consequence since targets are mostly tumor. The only exception is when the hotspot within the PTV also intersects an OAR.
4. Critical Organ Doses: Respect all critical organ dose-volume limits.
5. High-Dose Spillage:

[figure not shown]
- a. Location: Any dose > 105% of the prescription dose should occur within the PTV and not within the normal tissues outside the PTV.
- b. Volume: Acceptable isodose distributions should be as conformal as possible. To this end, the ratio of prescription isodose volume to PTV should be as small as possible.
  - i. The ratio of the prescription isodose volume to the PTV volume should be < 1.2. Acceptable variations include a ratio of 1.2-1.5. Ratios above 1.5 will be considered unacceptable variations. The prescription line for each lesion will be contoured for calculation of this ratio. The prescription line will be labelled as V\_5000 with the 5000 changing to reflect the prescription dose in cGy.
  - ii. Guidelines for the ratio of the 50% prescription isodose volume to the PTV volume (R50%) and for the maximum dose at 2cm (D2cm) from the PTV are given in table below.
  - iii. Given that conformal tumor coverage is often more difficult to achieve in lung than in more homogeneous organs, these ratios should serve as a guide for liver, abdominal-pelvic, mediastinal/cervical lesions as well.

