### 7.3.9 Planning Priorities

Every attempt should be made to successfully satisfy all of the planning goals and OAR criteria. In some circumstances, it may not be possible to meet all the ideal criteria, leading to plans in the Variation Acceptable range. Thus, suggested priority of planning goals in order of importance is as follows:

1. Respect spinal cord, cauda equina, sacral plexus and brachial plexus dose constraints.
2. Meet dose “compactness” constraints including the prescription isodose surface coverage, high-dose spillage (location and volume), and intermediate dose spillage (D2cm, and R50%) as these define the aim in using SBRT. Dose compactness should be assessed for plans based on treatment dose for a single lesion at a time.
3. Meet critical structure constraints other than those listed in 1. OAR dose constraints should be met based on composite dose planning. Unacceptable deviations should be avoided in all cases.
4. In cases where PTV coverage cannot be achieved while avoiding unacceptable deviations to OAR, coverage of a section of PTV including or immediately adjacent to the OAR may be as low as 70% of the prescription dose ONLY in this situation.

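### For lung, liver and renal cortex, the Table 6 note ends acceptable variation at 110% of the table value, but section 7.3.15.3 ends it at 110% of the prescription (14.85 Gy against 33 Gy for the 13.5 Gy lung rows)

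*Combined protocol and SAP*

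**What the plan says.** Table 6 (section 7.3.13) lists three parallel organs, each with a dose tied to a volume:

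- total lung: 13.5 Gy for the 37% row and the 1000 cc row, 12.5 Gy for the 1500 cc row
- renal cortex: 17.5 Gy, 200 cc
- liver: 15 Gy, 700 cc

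The note below the table says: "Doses to parallel OAR up to 110% of the values listed in the table will be an acceptable variation". A further note adds a minimum spared-volume check for these organs, with 1000 cc of lung at 1350 cGy as its example.

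Section 7.3.15.3 covers the case where the constraints cannot be met. It says: "Doses to parallel OAR exceeding 110% of the dose prescribed to the PTV will be scored as unacceptable deviations". It then adds: "Doses in the range between the numbers in the tables and unacceptable deviation will be considered acceptable variations".

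The body of section 7.3.13 has a third wording: "For parallel OAR, exceeding the doses by more than 110% of the prescribed dose will be considered unacceptable". Taken literally this cannot be applied, but its reference dose is the prescription, as in 7.3.15.3.

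The label of unacceptable deviation has a use. Priority 3 of section 7.3.9 says: "OAR dose constraints should be met based on composite dose planning. Unacceptable deviations should be avoided in all cases". Priority 4 begins "In cases where PTV coverage cannot be achieved while avoiding unacceptable deviations to OAR" and allows coverage beside the organ to fall to 70% of the prescription.

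**The concern.** The two rules measure the same excess against different reference doses. The Table 6 note uses the organ's own constraint. Section 7.3.15.3 uses the dose prescribed to the target, which is about twice as large and changes with the regimen, while the constraints do not. No section says which rule governs.

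The practical case is a plan whose lung dose stays above the Table 6 value after every planning effort. Suppose the constrained lung volume is at 20 Gy. That is outside the range the note accepts and inside the range 7.3.15.3 accepts. Two people scoring the plan could reach different answers, each with protocol text in support. Table 6 names pneumonitis as the outcome to be avoided for the 13.5 Gy lung rows, and pneumonitis is one of the focus toxicities in the run-in rule of section 12.1. A scoring limit that seldom binds is therefore badly placed here.

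**Working it through.** The plan states no computed ceiling to reproduce, so the check is arithmetic on its own inputs.

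**Inputs.** Table 6 values: 13.5, 12.5, 15 and 17.5 Gy. Prescription: 6 Gy x 5 = 30 Gy (section 3.3). Fallback after the run-in: 5 Gy x 5 = 25 Gy (section 12.1).

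**Formulas.** Ceiling under the Table 6 note = 1.10 x table value. Ceiling under 7.3.15.3 = 1.10 x prescription, which is 1.10 x 30 = 33 Gy or 1.10 x 25 = 27.5 Gy for every parallel organ.

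| Row | Note ceiling | 7.3.15.3 ceiling, 30 / 25 Gy | Ratio to note ceiling, 30 / 25 Gy |
|---|---|---|---|
| Lung, 13.5 Gy rows | 1.10 x 13.5 = 14.85 Gy | 33 / 27.5 Gy | 2.22 / 1.85 |
| Lung, 12.5 Gy row | 1.10 x 12.5 = 13.75 Gy | 33 / 27.5 Gy | 2.40 / 2.00 |
| Liver | 1.10 x 15 = 16.5 Gy | 33 / 27.5 Gy | 2.00 / 1.67 |
| Renal cortex | 1.10 x 17.5 = 19.25 Gy | 33 / 27.5 Gy | 1.71 / 1.43 |

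As a share of the table value, 7.3.15.3 accepts from 27.5/17.5 = 157% (renal cortex, 25 Gy) to 33/12.5 = 264% (lung 12.5 Gy row, 30 Gy). The note accepts 110%.

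**Which ceiling is plausible.** Section 7.3.8 says: "Any dose > 105% of the prescription dose should occur within the PTV and not within the normal tissues outside the PTV". That confines dose above 1.05 x 30 = 31.5 Gy, or 1.05 x 25 = 26.25 Gy, to the target volume. Both figures lie below the 7.3.15.3 ceilings of 33 and 27.5 Gy. In a plan that follows 7.3.8, parallel-organ tissue outside the target cannot breach 7.3.15.3. Only tissue inside a target volume could, and the parallel rows concern large volumes such as 37% of lung.

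**Serial organs.** The note and 7.3.15.3 agree on these: both use 105% of the dose prescribed to the target. Section 7.3.13 explains that some of these organs may lie against the target. The parallel rows have a different form, a moderate dose tied to a large volume or to a volume spared, and a multiple of the prescription does not fit it.

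**The case against.** The case against has five parts.

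1. **The planning text already protects these organs.** Section 7.3.6.1 makes the choice of thoracic lesions depend on meeting the organ constraints. Sections 7.3.7 and 7.3.8 require the constraints to be kept, and priority 3 of 7.3.9 repeats it. This stands. It confines the conflict to an excess that remains after planning, which 7.3.9 and 7.3.15.3 both foresee.
2. **The note does not call doses above 110% of the table value unacceptable.** Read literally, its range sits inside the range of 7.3.15.3. This also stands, so a flat contradiction would be too strong a claim. But a stated upper end to acceptable variation has little purpose if the range runs on to more than twice that dose for most rows.
3. **Two places use the prescription and one uses the table.** True: 7.3.13, though garbled, sides with 7.3.15.3, and 7.3.15.3 is the compliance section. That the note is the intended rule is an inference from the form of the rows and from the 105% rule. No section states it.
4. **Coverage can be lowered anyway.** Section 7.3.15.2 scores target coverage of 70-95% as an acceptable variation with no condition attached. A reader might infer that the coverage relief in 7.3.9 becomes empty for lung if 7.3.15.3 governs. The documents do not support that, because a planner may reduce coverage to meet Table 6 under either rule.
5. **No analysis uses the scores.** Section 12 does not refer to them, and response evaluability in 12.6.2 depends on one cycle of systemic therapy and completed radiation. This stands.

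**Conclusion.** The mismatch is real and should be corrected. For parallel organs the end of acceptable variation is 13.75 to 19.25 Gy under the Table 6 note. Under 7.3.15.3 it is 33 Gy, or 27.5 Gy on the fallback regimen, a factor of 1.4 to 2.4. The conflict arises by clear implication and concerns only the ceiling and scoring of a residual excess. The prescription-based ceiling is the less credible of the two.

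This rests on total prescriptions of 30 and 25 Gy, and on reading the note's 110% as the end of its acceptable range.

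A reader might infer that the protocol licenses lung doses of 33 Gy, or that the pneumonitis rate or the run-in decision is affected. The documents do not support this. The ratios compare scoring limits and are not doses any subject is expected to receive. The planning sections still point to Table 6, and the run-in rule counts toxicities without reference to deviation scores. Sample size and endpoints are untouched.

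**What to change.** In section 7.3.15.3, for parallel organs, replace the limit based on the prescription with 110% of the Table 6 value. Reword the parallel-organ sentence in the body of 7.3.13 to match. State that the 110% applies to the dose at which the constrained or spared volume is counted:

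- lung: less than 37% of the volume at 14.85 Gy, at least 1000 cc spared at 14.85 Gy, and at least 1500 cc spared at 13.75 Gy
- liver: at least 700 cc spared at 16.5 Gy
- renal cortex: at least 200 cc spared at 19.25 Gy

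The serial-organ rule can stay as it is. If any subjects have been treated, re-score their plans from the dose-volume histograms that section 7.3.12 requires.

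The cost is a short wording amendment and, where plans exist, the re-scoring. A few lung-heavy multi-site plans may need lower coverage beside the organ or one lesion fewer, so slightly less disease would be irradiated in those subjects.

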## 7.4 Availability

As the systemic chemotherapy agents (Carboplatin, Cisplatin, and Etoposide) employed in this study will be used according to their FDA-approved indications, they will be obtained through the various institutions taking part in this trial and billed to the subjects' insurance. Durvalumab will be supplied

by AstraZeneca. Radiation treatment will be delivered at the appropriate facilities within each participating institution.

### **7.5 Dosing Delays/Dose Modifications**

Dose-reductions up to Carboplatin AUC = 2.5, Cisplatin = 35mg/m^2, and/or Etoposide = 50mg/m^2 will be permitted during treatment at the discretion of the treating medical oncologist. There will be no dose-reductions for Durvalumab. Infusion times for chemotherapy and Durvalumab may be adjusted to improve tolerability, as per the treating medical oncologist.

Each 21-day cycle of Carboplatin/Cisplatin + Etoposide + Durvalumab may be delayed up to 4 weeks. Each 28-day cycle of single-agent Durvalumab may be delayed up to 6 weeks.

Every effort should be made to limit dose-reductions and delays in chemotherapy and immunotherapy.

All five fractions of radiation should be completed within 2-3 weeks of first radiation dose. Greater than 3 weeks is an unacceptable variation.

### **7.6 General Concomitant Medication and Supportive Care Guidelines**

All concomitant medications will be recorded and/or updated on subject medication log throughout the course of the study and saved in subject binder, if applicable.

#### **7.6.1 Prohibited Medications**

- Any investigational anticancer therapy other than those under investigation in this study.
- Any concurrent chemotherapy, radiotherapy, immunotherapy, or biologic or hormonal therapy for cancer treatment other than those under investigation in this study.
- EGFR TKIs
- Live attenuated vaccines
- Herbal and natural remedies which may have immune-modulating effects
- Immunosuppressive medications including, but not limited to, systemic corticosteroids at doses exceeding 10 mg/day of prednisone or equivalent, methotrexate, azathioprine, and tumor necrosis factor- $\alpha$  blockers

The following are allowed exceptions:

- Use of immunosuppressive medications for the management of IP-related AEs,
- Short-term premedication for patients receiving chemotherapy where the prescribing information for the agent requires the use of steroids for documented hypersensitivity reactions
- Use in patients with contrast allergies.
- In addition, use of inhaled, topical, and intranasal corticosteroids is permitted.

In addition, a temporary period of steroids will be allowed if clinically indicated and considered to be essential for the management of non-immunotherapy related events experienced by the patient (e.g., chronic obstructive pulmonary disease, radiation, nausea, etc.).

#### **7.6.2 Contraception**

The following restrictions apply while the patient is receiving study treatment and for the specified times before and after:

1. Female patient of child-bearing potential

Female patients of childbearing potential who are not abstinent and intend to be sexually active with a non-sterilized male partner must use at least 1 highly effective method of contraception (Table 7) from the time of screening throughout the total duration of the drug treatment and the drug washout period (90 days after the last dose of durvalumab monotherapy). Non-sterilized male partners of a female patient of childbearing potential must use male condom plus spermicide throughout this period. Cessation of birth control after this point should be discussed with a responsible physician. Periodic abstinence, the rhythm method, and the withdrawal method are not acceptable methods of birth control. Female patients should also refrain from breastfeeding throughout this period.

2. Male patients with a female partner of childbearing potential

Non-sterilized male patients who are not abstinent and intend to be sexually active with a female partner of childbearing potential must use a male condom plus spermicide from the time of screening throughout the total duration of the drug treatment and the drug washout period (90 days after the last dose of durvalumab monotherapy). However, periodic abstinence, the rhythm method, and the withdrawal method are not acceptable methods of contraception. Male patients should refrain from sperm donation throughout this period.

Female partners (of childbearing potential) of male patients must also use a highly effective method of contraception throughout this period (Table 7).

Females of childbearing potential are defined as those who are not surgically sterile (ie, bilateral salpingectomy, bilateral oophorectomy, or complete hysterectomy) or post-menopausal.

Women will be considered post-menopausal if they have been amenorrheic for 12 months without an alternative medical cause. The following age-specific requirements apply:

- Women <50 years of age would be considered post-menopausal if they have been amenorrheic for 12 months or more following cessation of exogenous hormonal treatments and if they have luteinizing hormone and follicle-stimulating hormone levels in the post-menopausal range for the institution.
- Women ≥50 years of age would be considered post-menopausal if they have been amenorrheic for 12 months or more following cessation of all exogenous hormonal treatments, had radiation-induced menopause with last menses >1 year ago, had chemotherapy-induced menopause with last menses >1 year ago.

Highly effective methods of contraception, defined as one that results in a low failure rate (ie, less than 1% per year) when used consistently and correctly are described in Table 7. Note that some contraception methods are not considered highly effective (e.g. male or female condom with or without spermicide; female cap, diaphragm, or sponge with or without spermicide; non-copper containing intrauterine device; progestogen-only oral hormonal contraceptive pills where inhibition of ovulation is not the primary mode of action [excluding Cerazette/desogestrel which is considered highly effective]; and triphasic combined oral contraceptive pills).

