17. Current or prior use of immunosuppressive medication within 14 days before the first dose of durvalumab. The following are exceptions to this criterion:

- a. Intransal, inhaled, topical steroids, or local steroid injections (e.g., intra-articular injection).
- b. Systemic corticosteroids at physiologic doses not to exceed 10 mg/day of prednisone or its equivalent.
- c. Steroids as premedication for hypersensitivity reactions (e.g., CT scan premedication). Premedication with steroids for chemotherapy is acceptable.

18. History of active primary immunodeficiency.

19. Receipt of live, attenuated vaccine within 30 days prior to the first dose of durvalumab

20. Female patients who are pregnant or breast-feeding or male or female patients of reproductive potential who are not willing to employ effective birth control from screening to 90 days after the last dose of durvalumab monotherapy.

21. Known allergy or hypersensitivity to durvalumab, etoposide, carboplatin, cisplatin, or any of their excipients.

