### 7.6.3 Blood Donation

Patients should not donate blood while participating in this study, or for at least 90 days following the last infusion of durvalumab.

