#### Paternal exposure

Male patients should refrain from fathering a child or donating sperm during the study and for 180 days after the last dose of durvalumab + any drug combination therapy or 90 days after the last dose of durvalumab monotherapy, whichever is the longer time period.

Pregnancy of the patient’s partner is not considered to be an AE. However, the outcome of all pregnancies (spontaneous miscarriage, elective termination, ectopic pregnancy,

normal birth, or congenital abnormality) occurring from the date of the first dose until 180 days after the last dose of durvalumab + any drug combination therapy or 90 days after the last dose of durvalumab monotherapy, whichever is the longer time period should, if possible, be followed up and documented.

Where a report of pregnancy is received, prior to obtaining information about the pregnancy, the Investigator must obtain the consent of the patient's partner. Therefore, the local study team should adopt the generic ICF template in line with local procedures and submit it to the relevant Ethics Committees (ECs)/Institutional Review Boards (IRBs) prior to use.

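### For men, section 7.6.2 and exclusion criterion 20 stop 90 days after durvalumab monotherapy, but section 13.1.4 runs to 180 days after the last combination dose if that is later

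*Combined protocol and SAP*

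**What the plan says.** Three places in the combined protocol and SAP set an end date for men.

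- **Section 7.6.2 (Contraception).** Non-sterilized men with a partner of childbearing potential use a condom plus spermicide from screening and "throughout the total duration of the drug treatment and the drug washout period (90 days after the last dose of durvalumab monotherapy". The sperm-donation bar has the same length: "Male patients should refrain from sperm donation throughout this period". The partner's own contraception is tied to that period too.
- **Section 4.3, exclusion criterion 20.** Men and women of reproductive potential must be willing to use effective birth control "from screening to 90 days after the last dose of durvalumab monotherapy".
- **Section 13.1.4 (Pregnancy, paternal exposure).** The restriction reads: "Male patients should refrain from fathering a child or donating sperm during the study and for 180 days". Those 180 days are counted from the final combination dose, and the alternative given is "or 90 days after the last dose of durvalumab monotherapy, whichever is the longer time period". The same rule sets the period for following partner pregnancies, namely those "occurring from the date of the first dose until 180 days after the last dose of durvalumab + any drug combination therapy", with the same 90-day monotherapy alternative if that ends later.

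Neither 7.6.2 nor criterion 20 mentions combination dosing or refers to 13.1.4, and no section is said to take precedence.

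For women, 7.6.2 counts from the same monotherapy dose and adds: "Cessation of birth control after this point should be discussed with a responsible physician".

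**The concern.** All subjects are planned to receive durvalumab with platinum and etoposide for four cycles before durvalumab alone, so the combination clause in 13.1.4 applies to this trial. A man counselled from the section headed Contraception could stop condom use, or donate sperm, while 13.1.4 still asks him to refrain. Site staff have two end dates in the current text and nothing that tells them which governs. The stake is the protection of participants and their partners. No endpoint, sample size or analysis depends on it.

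**Working it through.** The plan gives no figure to reproduce. The check compares the texts and then counts days on the planned schedule.

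**Texts side by side**

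| Item | 7.6.2 | Criterion 20 | 13.1.4 |
|---|---|---|---|
| Restricted for men | Condom use required; sperm donation barred | Birth control required | Fathering a child; sperm donation |
| Days after last combination dose | not mentioned | not mentioned | 180 |
| Days after last monotherapy dose | 90 | 90 | 90 |
| Which governs | only one rule | only one rule | the longer |

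Sperm donation has an end date in both 7.6.2 and 13.1.4, and the dates differ. Section 13.1.4 names no contraceptive method, so for contraception the conflict is one of effect: the section that names the method lets it stop while the other still asks men not to father a child.

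**Inputs**
- Last combination durvalumab dose: Day 64 (6.1.2.4).
- Monotherapy: Day 85, then every 28 days (6.1.2.5), so Days 85, 113, 141, 169.
- Assumption: the study period named in 13.1.4 ends at the last dose.

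**Formula.** With M the day of the last monotherapy dose, 7.6.2 ends on M + 90. The combination limit in 13.1.4 ends on 64 + 180 = Day 244. Gap = max(0, 244 − (M + 90)).

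| Last monotherapy dose | M | 7.6.2 ends | 13.1.4 ends | Gap (days) |
|---|---|---|---|---|
| First | 85 | 175 | 244 | 69 |
| Second | 113 | 203 | 244 | 41 |
| Third | 141 | 231 | 244 | 13 |
| Fourth | 169 | 259 | 259 | 0 |

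The 180-day limit is the later one whenever M falls before Day 244 − 90 = 154, which on schedule means three or fewer monotherapy doses.

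**How far the figures move**
- Counting from the last etoposide dose (Day 66, limit Day 246): 246 − 175 = 71, 246 − 203 = 43, 246 − 231 = 15, and zero at the fourth.
- First monotherapy dose delayed by the maximum six weeks in 7.5 (Day 127): 244 − 217 = 27.
- Visit windows of 7 days, fixed around nominal days: cycle 4 falls on Day 57 to 71, so the limit is Day 237 to 251. First dose: 237 − 182 = 55 to 251 − 168 = 83. Second: 237 − 210 = 27 to 251 − 196 = 55. Third: 0 (237 − 238 is negative) to 251 − 224 = 27. Fourth: 0, since even 251 − 252 is negative.
- Visit windows running from dose to dose instead: the fourth dose could fall as early as 78 + 3 × 21 = Day 141, and the gap could reach 251 − 231 = 20 days.

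**Men who stop in cycles 1 to 4.** A last combination dose on Day 1, 22, 43 or 64 gives a 13.1.4 end on Day 181, 202, 223 or 244. Section 7.6.2 has no monotherapy dose to count from, so its end date is undefined and no gap can be computed without adding words to it.

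**The case against.** The strongest reply is that 13.1.4 already holds the stricter rule, so careful staff would follow it, and that the longer period sits in an adverse-event reporting section worded generically for any drug combination. Either section could be the outdated one. The second part stands: the documents show a conflict but do not prove that 180 days is correct. The first part does not remove the problem, because the section on contraception and the eligibility criterion both give the shorter period and neither points to 13.1.4.

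It is also fair to say that only the sperm-donation dates collide outright, and that the day counts depend on the assumptions listed. Both are accepted.

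Following partner pregnancies beyond the contraception period is a surveillance choice and contradicts nothing by itself. It shows only that the 180/90 rule is used twice in 13.1.4.

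A reader might infer a 90-day shortfall for men who stop in cycles 1 to 4. That comes from reading 7.6.2 as 90 days after the last durvalumab dose of any kind, which it does not say. Taken literally, those men have an undefined or open-ended period.

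The consent pages were not among the documents reviewed, so what participants are told is unknown.

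**Conclusion.** The inconsistency is real and limited to men whose last durvalumab dose comes early. On the nominal schedule the shorter rule ends 69, 41 or 13 days before the longer one for a last dose at the first, second or third monotherapy visit, and the two coincide from the fourth. For men who stop in cycles 1 to 4, 7.6.2 supplies no end date.

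This rests on the last combination dose being durvalumab on Day 64, on no delays, and on the study period ending at the last dose. If that period includes follow-up (two years after removal from study, section 7.8), the gaps are larger and one can appear after the fourth dose as well. The zero gap at the fourth dose also need not survive visit windows that run from dose to dose. The number of men affected cannot be estimated, because the documents give no sex or age mix.

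A reader might infer a matching safety error for women, to be cured by a 90-day limit from the last durvalumab dose, as section 7.6.3 does for blood donation ("or for at least 90 days following the last infusion of durvalumab"). The documents do not support that. For women who never reach monotherapy the literal wording leaves the restriction open-ended, which errs towards protection. No section supports 90 days after combination dosing for contraception in women, and such a limit would be less protective than the present text. The period for these women is a question for safety staff.

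The text should be corrected, but nothing in the trial's statistical design or analysis changes.

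**What to change.** In 7.6.2 and exclusion criterion 20, state for men the stricter rule already in 13.1.4: 180 days after the last combination dose or 90 days after the last monotherapy dose, whichever is longer. Apply it to condom use, the partner's contraception and sperm donation.

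Ask the sponsor's safety staff to confirm the figure and to say whether the last combination dose means durvalumab or the last etoposide dose of that cycle. If they prefer another figure, put it in all three places. Ask them also what period applies to women who stop before monotherapy; do not set a 90-day limit for those women without that answer. Check that the consent form matches.

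The cost is a wording amendment, one consultation with safety staff and a consent-form check. No visits, procedures or subjects are added.
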